Material and Methods	
Inclusion
 
 
- patients <math>\geq</math> 18 years old
 
- with a diagnosis of metastatic GIST (metastatic at diagnostic or metastatic relapse)
 
- From 1990 to 2018
 
- with histological review performed by members of the pathological sub-committee of the GSF-GETO
 
- treated in one of the participating national reference network centers members of the GSF-GETO
 
- included in the prospectively maintained database of the GSF-GETO: the ConticaGIST
 
 
Methods
 
Descriptive data (see SARCOMABCB DICTIONNARY)
 
 
- Initial patients characteristics: age, gender, PS
 
- tumor characteristics : date, histology, location, size, mitotic count, miettinien classification, mutational status
 
- Initial treatment : initial surgery type, date, margins, tumor spillage, adjuvant systemic treatment (start and stop date)
 
- Metastatic disease characteristics : date, PS, location of metastasis
 
- Treatment in the metastatic setting : molecule used (start and stop date, best RECIST response), locoregional treatment performed, inclusion in a clinical trial
 
- Latest status : date, patient lastest Status, tumor latest status
 
 
Survival data
 
 
- Time to next treatment (TNT) TNT defined as the time from the systemic treatment onset to the next treatment or death due to any cause, whichever came first. When neither death nor new systemic therapy is observed, TNT is censored at the date of last patient contact.
 
- Overall survival in the metastatic setting (OS) defined as the interval between the diagnosis of metastatic disease or the first-line systemic therapy onset and the time of death. When death is not observed, OS is censored at the date of last patient contact.
 

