Statistics	
Statistical analysis of the baseline demographics and clinical outcomes will be based on all data available up to the cut-off date of December 31, 2018. Descriptive statistics will be used to show the distribution of variables in the population. Multivariate logistic regression models will be used to identify biological and clinical factors associated with the type of treatment received and with the probability of survival 5 years after the diagnosis of metastases. Follow-up times will be described as median values based on the inverse Kaplan–Meier estimator. Prognostic factors of TNT and OS will be identified using Cox proportional hazard models. The variables included in the univariate and multivariate analyses are the descriptive data.

	The correlation between TNT and OS will be evaluated at each of the four first-lines of metastatic chemotherapy by a Spearman rank correlation coefficient and expressed as a value between 0 (no association) and 1 (perfect association). We will use a reviewed copula-based approach that introduces an iterative multiple imputation method for the estimation of the correlation coefficient. The data will be analyzed using the SAS v9.3 and R v3.3 software packages.
Timeline	February 2019 : end of collection of data and updating of the conticaGIST March - April 2019 : first version statistical analyses
Ref	
 
 
 
 

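### The TNT–OS Spearman coefficient is given a 0-to-1 scale with 0 as no association, but its range is -1 to 1 and TNT lies inside OS, so the no-information value is above 0 and differs by line

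*Combined protocol and SAP*

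**What the plan says.** Three parts of the combined protocol and SAP bear on this.

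- **TNT** (Material and Methods, Survival data): "TNT defined as the time from the systemic treatment onset to the next treatment or death due to any cause, whichever came first". If neither event is seen, it is censored at last contact.
- **OS** (same section): "the interval between the diagnosis of metastatic disease or the first-line systemic therapy onset and the time of death". Two origins are offered, and both precede or coincide with line 1. It too is censored at last contact.
- **Correlation** (Statistics): "The correlation between TNT and OS will be evaluated at each of the four first-lines of metastatic chemotherapy". The measure is described as obtained "by a Spearman rank correlation coefficient and expressed as a value between 0 (no association) and 1 (perfect association", and the estimator is described thus: "We will use a reviewed copula-based approach that introduces an iterative multiple imputation method for the estimation of the correlation coefficient".

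The plan gives no reference value for the overlap between the two times. It plans no analysis of survival after TNT ends and sets no threshold for reading the coefficient.

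**The concern.** TNT ends at or before death. Provided a metastatic line starts on or after the OS origin, its TNT is a piece of the OS interval. Correlating a piece with the whole gives a positive value through the shared time alone. A reader who follows the printed scale would take a coefficient of, say, 0.6 at line 1 as a substantial association. That value can arise when TNT carries no information on what happens after the next treatment starts.

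The no-information value also depends on how large TNT is relative to the rest of OS, and this changes from line to line. Four coefficients set side by side could appear to show a weakening or strengthening relation where none exists. Separately, a scale that begins at 0 has no place for an inverse relation.

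**Working it through.** **Figures in the plan.** The documents state no expected coefficient, sample size, median or share of lines ended by death, so there is nothing to reproduce. Every distribution and duration below is an assumption, shown as a range.

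**Structure.** Let T be TNT at a line, R survival after TNT ends (R = 0 if death ends the line), and E the time from the OS origin to the start of the line.

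- In general, OS = E + T + R.
- At line 1 with OS from first-line onset, E = 0 and OS = T + R.
- At line 1 with OS from metastatic diagnosis, E is the gap before treatment.
- At lines 2–4, E includes all earlier lines.

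No information means that T is independent of R and, where E is present, of E.

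**Analytic check at line 1.** Take independent exponential T and R, no line ended by death, and r = mean R / mean T. The Pearson correlation of T with T + R is 1/√(1 + r²).

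- r = 0.5: 1/√1.25 = 0.894 (simulated 0.895)
- r = 1: 1/√2 = 0.707 (simulated 0.705)
- r = 2: 1/√5 = 0.447 (simulated 0.446)

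**Spearman at line 1, OS from first-line onset.** 400,000 simulated patients per setting, no censoring, T independent of R:

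| Median TNT / later survival (months) | No line ended by death | 40% ended by death |
|---|---|---|
| 10 / 30 | 0.36 | 0.46 |
| 20 / 30 | 0.55 | 0.62 |
| 30 / 30 | 0.67 | 0.72 |
| 30 / 15 | 0.83 | 0.86 |

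Weibull or lognormal times with T and R identically distributed give 0.64 to 0.68. A gap before line 1 averaging half of mean TNT lowers 0.67 to 0.61 (equal means, no line ended by death).

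**Lines 1 to 4.** Exponential times, mean 10 months of survival after line 4, 15% of lines ended by death, everything independent:

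| Assumed mean TNT, lines 1–4 (months) | OS from line 1 onset | OS from each line's start |
|---|---|---|
| 24 / 8 / 5 / 4 | 0.75, 0.29, 0.18, 0.15 | 0.75, 0.50, 0.42, 0.42 |
| 36 / 8 / 5 / 3 | 0.85, 0.23, 0.14, 0.09 | 0.85, 0.51, 0.44, 0.35 |
| 12 / 12 / 12 / 12 | 0.37, 0.39, 0.40, 0.41 | 0.37, 0.44, 0.54, 0.72 |

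In these runs the Spearman coefficient of T with R is about 0.00 at every line. The no-information value therefore depends on the line, on the OS origin and on how TNT changes across lines. The second column uses an OS origin that the plan does not define. It is shown because a per-line analysis might adopt it.

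**Estimator.** All the values above come from complete data. As described, the copula and imputation step estimates the coefficient. Nothing in its description removes the shared time.

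**The case against.** The best defence is that the coefficient is descriptive. A value of 0 does mean no rank association between TNT and OS, and the coefficient validly describes the marginal relation. Whether TNT predicts survival after TNT is a different question. The correlation is not among the listed objectives, and no comparison of the four lines is announced. All of this stands, and it limits the point to interpretation. It does not rescue the printed range, and it does not supply a reader with the value that overlap alone would produce.

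A reader might infer four stronger things that the documents do not support.

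- **That OS equals TNT plus later survival at every line.** The OS definition starts at metastatic diagnosis or first-line onset, so this identity holds only at line 1 counted from first-line onset.
- **That the coefficient is large at every line, or positive whatever the truth.** With OS from line 1 and shortening TNT, lines 2–4 have no-information values of only about 0.1–0.3. With 20% of lines ended by death and a copula correlation of -0.3 between TNT and later survival, line 1 still gives +0.21 to +0.78 over the four median settings, but lines 2–4 give about 0.02 to 0.17. At -0.5, lines 2–4 give about -0.02 to 0.08.
- **That a significance test against 0 would almost always reject.** The plan states no null hypothesis, alpha or threshold for this coefficient.
- **That the study claims TNT as a surrogate for OS.** It does not.

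**Conclusion.** The point holds in a limited form and should be corrected. The stated range is wrong for Spearman's coefficient whatever is assumed. The containment of TNT in OS follows from the definitions, given that lines start on or after the OS origin. The size does not follow from the documents. At line 1 with OS from first-line onset, the no-information value is about 0.36–0.86 over the settings tried. At lines 2–4 with TNT shortening by line, it is about 0.1–0.3 from first-line onset, or about 0.4–0.5 from each line's start. The second of these widens to 0.33–0.59 over the two declining sets of means with 0–30% of lines ended by death. With equal mean TNT at all lines the pattern changes, to about 0.4 and 0.44–0.74 respectively.

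The four coefficients should therefore not be compared with each other, nor read as evidence that TNT predicts later survival.

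**What to change.** 1. State the range as -1 to 1, and say that TNT is contained in OS, so that 0 is not the no-information value.
2. Fix one OS origin for this analysis at each line.
3. Beside each coefficient, report its reference value under independence of TNT and later survival. Simulate it from the fitted distributions and the share of lines ended by death, for that same OS origin. Where OS starts before the line, include the time before the line; a reference built from TNT and later survival alone would be too high at lines 2–4.
4. Per line, add a Cox model of survival from the start of the next line on completed TNT (log or spline), among patients who start one. Base any statement that TNT predicts later survival on this model.

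As a check on item 4, a simulation with medians of 20/30 months, 20% of lines ended by death and uniform censoring at 12–180 months, tested at 5%, gave rejection rates under no information of 4.9%, 4.5% and 5.4% at 50, 100 and 300 patients. With a copula correlation of 0.3 they were 34%, 61% and 93%.

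The cost is some SAP wording, a short simulation and one extra model per line. The drug start dates and latest-status date needed are already listed for collection. The added model excludes patients who die on the line or never start another, so it supplements the full-cohort coefficient and does not replace it.

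### TNT at each line is a time segment of OS, so a Spearman correlation of 0 is not the no-association value for this pair

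*Combined protocol and SAP*

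**What the plan says.** All references are to the combined protocol and SAP.

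- **Material and Methods, Survival data (TNT):** "TNT defined as the time from the systemic treatment onset to the next treatment or death due to any cause, whichever came first". Censoring: "When neither death nor new systemic therapy is observed, TNT is censored at the date of last patient contact".
- **Material and Methods, Survival data (OS):** "defined as the interval between the diagnosis of metastatic disease or the first-line systemic therapy onset and the time of death". Censoring: "When death is not observed, OS is censored at the date of last patient contact". Two origins are offered, and neither is specific to lines 2 to 4.
- **Statistics (measure):** "The correlation between TNT and OS will be evaluated at each of the four first-lines of metastatic chemotherapy by a Spearman rank correlation coefficient", on the scale quoted as "expressed as a value between 0 (no association) and 1 (perfect association".
- **Statistics (estimation):** "We will use a reviewed copula-based approach that introduces an iterative multiple imputation method for the estimation of the correlation coefficient".

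The plan does not mention the overlap between the two endpoints and gives no reference value for no association. It does not say how OS is timed when the TNT of a later line is analysed. The Objectives section lists TNT and OS, but not their correlation.

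**The concern.** Take one line and count both endpoints from its onset. Then OS = TNT + survival after the TNT event. A patient who dies without a further treatment has TNT = OS exactly. If OS is counted from first-line onset or from metastatic diagnosis, other segments are added, but the line's TNT is still one of the pieces that make up OS. A part correlates with the whole that contains it, even when it is unrelated to the remainder.

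Two readings are then at risk. A moderate positive coefficient would be taken as evidence that TNT tracks survival when some or all of it is overlap. A change in the coefficient from line 1 to line 4 would be taken as a change in association when it may only reflect how much of OS each line's TNT occupies.

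**Working it through.** **Inputs.** The endpoint definitions, the choice of Spearman's rho and the four lines come from the document. It states no figure that could be reproduced here: no medians, death share, sample size or expected correlation. All numerical inputs below are therefore assumptions, shown as ranges. Results are from large simulations without censoring, with no association built in unless stated.

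**Step 1. One case by hand.** Let TNT = T and later survival = P be independent exponentials with mean 1, no deaths at the TNT event, and OS = T + P. For continuous variables rho = 12·E[F(T)·G(OS)] − 3, with F(t) = 1 − e^(−t) and G(s) = 1 − (1 + s)e^(−s).

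E[F·G] = 1 − 1/2 − 1/2 + E[e^(−2T)·e^(−P)·(1 + T + P)] = (1/3)(1/2) + (1/9)(1/2) + (1/3)(1/4) = 11/36.

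So rho = 12 × 11/36 − 3 = 2/3, although T and P are independent.

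**Step 2. Same line onset for both endpoints, varying the shares.** P is independent of T; a share q of TNT events are deaths (P = 0).

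| Mean later survival ÷ mean TNT (patients who continue) | 0.5 | 1 | 1.5 | 2 | 3 |
|---|---|---|---|---|---|
| rho, q = 0 | 0.83 | 0.67 | 0.55 | 0.47 | 0.36 |
| rho, q = 0.3 | 0.85 | 0.70 | 0.59 | 0.51 | 0.42 |

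**Step 3. Independent latent times.** Let X (time to next treatment) and D (death) be independent exponentials, TNT = min(X, D) and OS = D. With 5, 10, 20, 30 and 50% of TNT events being deaths, rho is 0.07, 0.14, 0.27, 0.39 and 0.60. Here the death share q fixes the ratio: averaged over all patients, mean later survival is (1 − q)/q times mean TNT. That is 0.95/0.05 = 19 at q = 0.05 and 0.90/0.10 = 9 at q = 0.10. The low values thus belong to settings where TNT is a very small part of OS.

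**Step 4. OS from first-line onset, lines 1 to 4.** Independent exponential segments with assumed means 24, 8, 5 and 4 (any one time unit), then a residual; no deaths at line end.

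| Residual mean | Line 1 | Line 2 | Line 3 | Line 4 |
|---|---|---|---|---|
| 6 | 0.82 | 0.31 | 0.20 | 0.16 |
| 24 | 0.62 | 0.22 | 0.14 | 0.11 |

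If 10 to 30% die at the end of each line, the first row hardly changes (line 1 stays at about 0.8). Under those death shares and the same means, restarting OS at each line's own onset gives 0.51 to 0.62 at lines 2 to 4. The choice of origin alone therefore moves the no-association value from 0.15–0.31 to 0.51–0.62.

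**Step 5. Sign.** With a negative dependence between T and P (Gaussian copula, parameter −0.5), rho between TNT and OS is +0.43 when mean later survival equals mean TNT, and −0.15 when it is four times as long. With −0.9 and four times it is −0.65. Values below 0 are possible, and a positive value can coexist with a negative relation between TNT and later survival.

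**Step 6. The quantity for which 0 is right.** With the segments of Step 4 and deaths at line end, TNT against survival after the TNT event gives rho = 0.00 at every line.

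**Step 7. A limit on the remedy.** Survival after TNT is followed only for the time left after TNT, so long TNT leaves little or no follow-up. With unit exponential margins, a Gaussian copula of 0.5 and censoring uniform on 0 to 3, Kaplan–Meier survival after TNT at time 1 was 0.28 against a marginal value of 0.37. Restricting to patients who start a next treatment lowered rho from 0.48 to 0.42.

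**The case against.** The strongest reply has four parts.

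1. **Size.** A reader might infer that the null correlation is strongly positive at every line. The documents do not support that. Values of 0.36 to 0.85 require OS to restart at each line's onset, which the OS definition does not say. With first-line onset as origin, lines 2 to 4 can lie well below 0.36 (Step 4), and line 1 can too if TNT is a small part of OS (Step 3). This part stands; only the direction is certain.
2. **Scale.** A reader might infer that the whole scale is wrong. That is too broad: 0 and 1 are the usual reference values of Spearman's rho for two quantities that do not overlap. The faults are the use of 0 as the reference for this pair and the omission of negative values. The omission alone does little harm if the pair is positively related.
3. **Copula.** It is tempting to say that the planned copula method ignores the constraint TNT ≤ OS. The plan does not name the copula or describe how it treats that constraint or the ties at death, so this cannot be asserted. Nor can the method be credited as a remedy: an exact estimate of rho would still be read against the wrong zero.
4. **Use.** The study is descriptive, the correlation is not a listed objective, and no surrogacy claim, threshold or decision rests on it. This stands and limits the importance of the point.

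None of these removes the overlap or supplies a reference value.

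**Conclusion.** The point holds in direction. From the plan's own definitions, TNT and OS share time and death events, so the no-association value of their rank correlation is above 0, and it was so in every scenario tried without built-in association. Its size is not established by the documents. It depends on TNT's share of OS, the share of TNT events that are deaths, the line and the OS origin. Under assumed independent exponential segments it spans about 0.1 to 0.85. With OS from first-line onset and the assumed means of Step 4 it is 0.62 to 0.82 at line 1 and 0.11 to 0.31 at lines 2 to 4. A falling coefficient across lines would therefore not by itself show a weakening association. The consequence is confined to the interpretation of this one analysis; the descriptive objectives and the separate TNT and OS estimates are unaffected.

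**What to change.** In the Statistics section:

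1. State that rho runs from −1 to 1, and remove the statement that 0 means no association for TNT against OS.
2. State one OS origin for each line's analysis. Either first-line onset or the line's own onset can be used, but the reference value differs, so the choice must be fixed in advance.
3. Print beside each TNT–OS coefficient the value expected when survival after TNT is independent of TNT, under the same origin and death share, and interpret only the excess.
4. Add, as a supporting analysis at each line, the rank correlation of TNT with survival after the start of the next treatment, among patients who start one.
5. For items 3 and 4, use a method that allows for earlier censoring of later survival when TNT is longer, for example an imputation model for later survival that conditions on TNT. A plain Kaplan–Meier redraw is biased when the two are related (Step 7).
6. Say how the copula method treats TNT ≤ OS and the ties at death.

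**Cost.** No new data: treatment start dates and latest status are already collected. The work is more than a change of wording, because the imputation model has to be specified and a reference value computed for each line. The headline association will look less favourable, and the supporting analysis covers only patients who reach the next line.
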